##### **Study design:**

The study will take place over a period of 27 months. The recruitment phase will last approximately 24 months and each patient will participate for approximately 3 months.

At the inclusion visit (D0), the investigator will ask the patient whether he would like to participate in the study and will obtain his written consent. Refusal to participate including the reason if available will be collected in a register specific to this study (study register). The collected data will allow any selection bias to be identified.

Each patient agreeing to participate in the study will be randomised by receiving a randomisation number and assigned to its corresponding group. Randomisation will be done by envelopes (See Section 7.5). The investigators or medical team will send a randomisation fax to Patientys for each patient included in the study. Patientys will forward the anonymised data to the contract research organisation (CRO) in charge of the data monitoring.

The randomisation will follow a 3:1 ratio and the patients will be included in one of the following 2 groups:

- Group without 'remote additional personalised nurse-led follow-up': patients will receive the healthcare given routinely by their medical team (100 patients).

OR

- Group with 'remote additional personalised nurse-led follow-up': patients will receive telephone calls from a nurse in addition to the healthcare given routinely by their medical team (300 patients).

All the patients will be seen according to normal practice by the study medical team. In this study, 3 data collection time-points at monthly intervals are defined (D30, D60, D90); however the frequency of visits should not be adjusted and the medical team should maintain his routine practice (example: if the investigator is used to see the patient on D15, the visit will still take place, but no information, except pharmacovigilance data, will be collected). As

such, the data from the closest defined visit will be reported in the case report form (CRF) at each time point (see Figure 1).

During the inclusion consultation, the medical team will provide the patient with a patient diary with all the main information regarding its treatment and in which he should report some information (see Section 6.2).

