The telephone calls will be made by a nurse from a company specialised in patients support called Patientys. Patients in the group with 'remote additional personalised nurse-led follow-up' will be contacted 8 times during the study (at D1, D7, D14, D21, D28, D44, D59 and D89, see Figure 1). The nurse will make sure that the treatment takes place in good conditions; she cannot intervene in the medical care of the patient, nor give answer to the questions relative to the disease or to the treatment of the patient. The medical team remains the privileged contact of the patient.

During the informed consent process, the patient may authorize a relative (i.e. a person he trusts and who can be among other, a family member, a friend or a housemate) to assist him during the nurse-led phone call. The first and last name of this person will be specified on the informed consent form.

During the first telephone call at D1, the nurse will confirm the enrolment of the patient in the study and will re-explain the calls schedule. Following this call, if the patient agrees to give the contact details of their physician and pharmacist, then the nurse will inform them, by letter or phone call, of the patient participation in the study.

During the following telephone calls, the nurse will perform a clinical evaluation by using a pre-established questionnaire and will collect treatment related AEs (see Section 6.2.3) as well as the pharmacovigilance (PV) information. After each telephone call, the nurse will establish a report.

The telephone call reports will be sent to the investigators on the same day of the nurse follow-up phone call.

The investigator will verify the severity of the AE and will determine the causal relationship with the oral targeted therapy.

- If case of serious adverse event (SAE), the investigator must complete and send immediately the serious adverse event (SAE) form (SAE form) to the CRO in charge of data monitoring (within 24h of the event). The causality will be determined by the investigator and recorded on SAE declaration form. In case of treatment exposure during pregnancy please refer to Section 5.3.2.2.
- In case of non-serious AE and/or of any other PV information, the investigator should complete and send the AEs page of the CRF to the CRO in charge of data monitoring within 7 days of the event. The causality will be determined by the investigator and recorded on the AEs page of the CRF.

[figure not shown]

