## **6.2 DETAILS OF DATA COLLECTION AT EACH VISIT/ PHONE CALL**

### **6.2.1 Inclusion (Incl. MV)**

During the inclusion consultation, the medical team will ask the patient to participate in this study. Written consent will be obtained; however if the patient refuses to participate in the study, the refusal with the corresponding reason, if available, will be documented in the study registry. The patient accepting to participate in the study will be randomised to receive or not a remote additional nurse-led follow-up during the follow-up period (randomisation ratio of 3:1).

The registration form must be completed and forwarded to Patientys by e-mail or FAX.

If the patient agrees to participate in the study, the investigator will collect the following data:

- Demographic information (age, gender, weight, height).
- NSCLC characteristics (date of first diagnosis, disease stage, performance status from the Eastern Cooperative Oncology Group [ECOG], biopsy date, type of mutation(s) detected, test/method used to assess mutation and previous treatments).
- Medical history, concomitant diseases, previous and concomitant treatment.
- Results of the complete physical examination: vital signs (heart and respiratory rate, blood pressure, temperature), and presence of any of the following symptoms: coetaneous, gastrointestinal, respiratory, ocular, cardiovascular and allergic.

As with any initiation of oral targeted therapy treatment, the medical team will counsel the patient on the oral targeted therapy, treatment schedule and precautions (lifestyle changes) to be taken in order to prevent treatment related adverse events, in addition to giving the patient a diary to report information related to the utilisation of healthcare services (telephone calls with or visits to their general practitioner or specialist, with any specialty).

During this consultation, and as per routine practice, the medical team will set the schedule of upcoming consultations. In this study, 3 data collection time-points at monthly intervals are defined (D30, D60, and D90). The frequency of visits should not be adjusted and the medical team should maintain his routine practice (example: if the investigator is used to see the patient on D15, the visit will still take place, but no information, except pharmacovigilance data, will be collected). As such, the data from the closest defined visit will be reported in the CRF.

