## 7. STATISTICAL METHODS AND DETERMINATION OF PATIENTS SAMPLE SIZE

### 7.1 STATISTICAL DESIGN

This is a routine clinical practice, randomised, open-label, multicentre, study.

Patients will be randomised in one of the following 2 groups:

- Group ‘without remote additional personalised nurse-led follow-up’: patients will receive the healthcare given routinely by the medical team (100 patients).
- Group with ‘remote additional personalised nurse-led follow-up’: patients will receive telephone calls from a nurse in addition to the healthcare given routinely by their medical team (300 patients).

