### **7.5            RANDOMISATION**

Patients will be randomised in one of the 2 study groups following a ratio of 3:1 (3 patients in the with 'remote additional personalised nurse-led follow-up' group for each one patient in the without 'remote additional personalised nurse-led follow-up'), and according to a list of randomisation previously defined.

This list will be generated before the start of the study according to all the following criteria:

- Blocks of different size: 4 and 8.
- Parallel groups.
- Including 2 treatment groups.
- Following a 3:1 ratio.

It will be implemented using a validated computer tool which allows generating a sequence of pseudo-random numbers and selecting of a number called 'seed randomisation', not communicated to operational involved in the project, to ensure the non-reproducibility and non-predictability of the generation of randomisation list.

The allocation of a patient to one study group or the other ('with remote additional personalised nurse-led follow-up' versus 'without remote additional personalised nurse-led follow-up' will be done sequentially within each centre using randomisation envelope. To limit selection bias in the absence of central randomisation, the blocks of randomisation will be of varying size (4 or 8).

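### No registration outside the site is required before the allocation envelope is opened, and no reconciliation of envelopes is planned, so no planned check would find a patient dropped after allocation.

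*Combined protocol and SAP*

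**What the plan says.** - **Allocation.** Section 7.5 says that allocation "will be done sequentially within each centre using randomisation envelope". It acknowledges the lack of a central system and names one safeguard: "To limit selection bias in the absence of central randomisation, the blocks of randomisation will be of varying size (4 or 8".
- **Order of events, Section 3.1 (Study design).** The text describes consent, then the randomisation number and group by envelope, then the notice: "The investigators or medical team will send a randomisation fax to Patientys for each patient included in the study". The next step is: "Patientys will forward the anonymised data to the contract research organisation (CRO) in charge of the data monitoring".
- **Order of events, Section 6.2.1.** The accepting patient is randomised, and the text then adds: "The registration form must be completed and forwarded to Patientys by e-mail or FAX". The contents of this form are not given.
- **Who receives the notice.** Section 3.1 also states: "The telephone calls will be made by a nurse from a company specialised in patients support called Patientys".
- **Blinding.** Section 7.1: "This is a routine clinical practice, randomised, open-label, multicentre, study".
- **Records planned at the site.** These are a register of refusals (3.1), a record of acceptance or rejection at D0 (Table 1), a filed copy of the consent (3.3.2), an identification number issued on consent (8.1) and a randomisation number (3.1).
- **When the CRO receives case report forms.** Section 8.3.1 has them posted once the patient has completed the study.

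**The concern.** With envelopes, concealment depends on the patient being committed to the trial before the arm is seen. A record held by someone outside the site, made before opening, is what shows that commitment. The protocol describes no such record. In an open-label trial the site and the patient know the arm at D0. A patient who is disappointed, or an investigator who is, can at that point decide not to go on, and the notice that leaves the site covers only patients who are included.

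The loss would come after randomisation and could depend on the arm, so the two groups would no longer be comparable by design. The refusal register is meant to reveal selection bias, but it is described as covering refusal to participate, not loss after allocation. The analysis would not bring the patient back either, because the primary population in Section 7.3 requires data on the primary criterion. Patients who leave on learning their arm may well differ in how they take their treatment, which is the primary endpoint.

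**Working it through.** **1. The steps side by side**

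| Step | What the protocol states | What it does not state |
|---|---|---|
| Consent | Written, filed; identification number issued (3.3.2, 8.1) | That anyone outside the site is told at this point |
| Envelope | Used in sequence within the centre (7.5) | Sealing, opacity, signing or dating on opening |
| First outside notice | Fax or form to the call-centre company, described after allocation (3.1, 6.2.1) | When it is sent relative to opening |
| CRO informed | Through the call-centre company (3.1) | Any direct notice of the enrolment from the site |
| Close-out | Audit or inspection possible (8.2, 8.3.3) | Return of envelopes, or their reconciliation with consents, register and faxes |

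The right-hand column is the gap. Block sizes of 4 and 8 affect what a site can guess about the next envelope. They have no bearing on what happens once it is open.

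**2. The plan's own figures (Section 7.6)**

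Inputs: means of 3000 and 3180 mg (difference 180 mg), SD 500 mg, two-sided 5% level, ratio 3:1. The power of the t-test from the noncentral t distribution is 79.9% at 81/243 and 80.4% at 82/246. The stated 82/246 evaluable patients is therefore reproduced and serves as the base below.

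**3. What selective loss could do (illustration only)**

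Suppose a fraction f of controls is dropped after opening, and their mean dose would have been D mg above the control mean. Neither f nor D is in the documents. The mean of the remaining controls falls by f/(1 − f) × D, and the group difference shifts by the same amount. The type I error is computed with no true effect, SD 500, 82 × (1 − f) controls (rounded) and 246 nurse-group patients.

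| f | D (mg) | Bias = f/(1 − f) × D | Share of 180 mg | Type I error |
|---|---|---|---|---|
| 5% | 250 | 0.0526 × 250 = 13 mg | 7% | 5.5% |
| 10% | 250 | 0.1111 × 250 = 28 mg | 15% | 7.0% |
| 10% | 500 | 0.1111 × 500 = 56 mg | 31% | 13.3% |
| 20% | 500 | 0.25 × 500 = 125 mg | 69% | 43.6% |

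If the dropped patients would have taken less than average, D is negative and the bias changes sign.

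**4. Would the overall arm ratio show it?**

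Blocking within centre makes the control count much less variable than independent allocation would. I simulated 75 centres with blocks of 4 and 8 equally likely (assumed), with either about 5 patients per centre or uneven centre sizes. The SD of the control count was about 4 to 5, against about 8.6 for independent allocation (√(400 × 0.25 × 0.75) = 8.66). Starting from 100:300:

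| Controls lost | Count observed | Two-sided p, blocking respected |
|---|---|---|
| 5 | 95 of 395 | about 0.4 |
| 10 | 90 of 390 | about 0.08 to 0.13 |
| 15 | 85 of 385 | below 0.02 |

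The ratio would not reveal a small loss and would tend to reveal a large one. It could not say which patients were lost.

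**The case against.** The strongest reply is that the site does not have a free hand. A dropped patient has a signed consent, an identification number and an acceptance record. Envelopes are used in sequence from a list drawn up beforehand, so a spent envelope with no reported patient leaves a missing number once the centre reports a later patient. Entering a consented patient as a refusal would contradict the signed form. All of this stands. A reader might infer that such a patient would leave no trace; the documents do not support that. What they lack is any instruction to compare these records.

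Four further points need care:

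- **Order.** A reader might infer that the protocol requires the envelope to be opened before anyone outside is told. It does not say so. The order is read from the sequence of the text and the name of the fax. The weak order is permitted, not prescribed.
- **Recipient.** A reader might see a conflict of interest in sending the fax to the company whose calls are under test. The text does not show one. The company needs prompt notice for the D1 call, the fax covers every included patient, and the company is not described as holding envelopes. The relevant point is only that the CRO hears second-hand.
- **Motive.** Section 3.2 gives limiting refusals as one reason for the 3:1 ratio. That makes it plausible that control is the less welcome arm, but it concerns refusal to take part, not withdrawal after allocation.
- **Arm ratio.** A reader might infer that the final ratio could never expose the problem. With blocking taken into account, a loss of 15 controls probably would show.

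Envelope handling may also be set out in a site manual that is not among these documents. If so, the protocol should cite it.

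**Conclusion.** The gap is real but procedural. As written, the protocol lets the arm be seen before anyone outside the site knows of the patient, and it assigns no one to account for opened envelopes. Varying block sizes do not cover this.

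The conclusion rests on two readings: that the envelopes are held at the centre, and that the notice follows allocation. Both fit Sections 3.1, 6.2.1 and 7.5, but neither is stated as a rule. There is no evidence that patients would in fact be dropped, and the size and direction of any bias are unknown. The 13 to 125 mg range above depends wholly on assumed values of f and D and shows only why a check is worth having. No figure in the plan is wrong on this account. The point is a change that should be made because it is cheap and cannot be made good afterwards.

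**What to change.** Amend Sections 3.1, 6.2.1 and 7.5 so that they give one sequence:

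1. After consent and the eligibility check, the site sends the CRO a registration notice with the patient number, consent date and number of the next envelope, and without the arm.
2. Only then is the envelope opened. It is signed and dated on opening, and the patient counts as randomised from that moment.
3. The arm is then sent to the CRO, and to the call centre for patients in the nurse group.
4. At close-out all envelopes, used and unused, are returned and reconciled with the CRO log, the consents and the refusal register. Every opened envelope is accounted for in the report of patient flow.

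Cost: a few minutes at D0, possibly a small change to the registration form (its contents are not given, so this cannot be judged from the documents), return of envelopes and one reconciliation at close-out. The sample size and the analysis do not change.

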**Figure 1 General study design**

At D1, the Patientys nurse will contact the general practitioner and the pharmacist of the patient in order to inform them of the patient's participation in the study.

MV : medical visit according to the routine practice of the centre (for example, if the investigator is used to seeing patients at D15, this consultation will still take place but no information, except pharmacovigilance data will be collected); NFPC: nurse follow-up phone call ; rand : randomisation ; D = day

**Patientys call-centre:**

PATIENTYS – DIRECTMEDICA  
[name]  
[name]

**CRO in charge of study logistic and administrative management and data monitoring :****3.2 DISCUSSION OF STUDY DESIGN, INCLUDING THE CHOICE OF CONTROL GROUP**

The main objective of this study is to evaluate the impact of an additional nurse-led telephone follow-up during routine clinical practice of patients with stage IIIb/IV NSCLC. Based on recommendations of the Plan Cancer, nurse-led follow-up of patients becomes more and more common in order to ensure a better patient care. The implementation of nurse-led telephone follow-up in this study fits into this approach.

The current study is a routine clinical practice study and aims to evaluate the care provided to the patient and particularly the impact of the implementation of a nurse-led telephone follow-up in the patients' standard of care. In this routine clinical practice study, all the procedures and the products prescribed are part of the common practice. Only a particular method of follow-up is added for some patients. This method of monitoring has only negligible risks and constraints to patients enrolled in the study. The impact of the nurse-led telephone follow-up during healthcare given routinely will be assessed in terms of treatment compliance.

A control group that includes patients without additional nurse-led follow-up is needed to assess the benefit of the phone calls. To minimise the risk of patient's refusal to participate in the study and to collect sufficient data for patients with additional telephone follow-up, randomisation will be unbalanced. A ratio of 3:1 will be used for randomisation, giving each patient a probability of 0.75 to be included in the group with nurse-led follow-up' in addition to the healthcare given routinely by the specialised physician.

**3.3 SELECTION OF STUDY POPULATION****3.3.1 Main diagnosis for study entry**

The study will be proposed to adult patients diagnosed with stage IIIb/IV NSCLC locally advanced or metastatic, with activating mutation(s) of EGFR and who are EGFR-TKI naïve.

**3.3.2 Inclusion criteria**

Patients will be eligible to enter the study if they meet all the following inclusion criteria:

- Male or female patient older than 18 years.
- Adult patient diagnosed with stage IIIb/IV NSCLC locally advanced or metastatic, with activating mutation(s) of EGFR and who is EGFR-TKI naïve.

- Patient for whom a decision of treatment with afatinib monotherapy has been taken in the frame of its marketing authorization.
- Out-patient.
- Patient having given written consent for participation in the study.
- Patient who is able to participate in the investigator's opinion.
- Patient affiliated with the French social security.

A copy of the written consent will be given to the patient, and the second copy will be filed in the study record.

### **3.3.3      Exclusion criteria**

Patients meeting one of the following criteria will participating not be eligible

- Patients participating in an interventional clinical study.
- Patients for whom a participation in an interventional clinical study is foreseen within 3 months following the study inclusion.
- Patients participating in a therapeutic education program.

### **3.3.4      Removal of patients from therapy or assessments**

Patients can decide to discontinue their participation in this study at any time.

Boehringer Ingelheim reserves the right to discontinue the overall study or in a particular centre for the following reasons:

- Inability to recruit the planned number of subjects across centres or in a particular centre.
- Evidence of information that could significantly affect the continuation of the study, or for other administrative reasons.
- Violation of Good Clinical Practice (GCP) or contract, by a study centre or an investigator, preventing the proper conduct of the study.

## **4.            TREATMENTS**

Not applicable.

## **5. EVALUATION CRITERIA**

### **5.1 PRIMARY ENDPOINT**

#### **5.1.1 Primary endpoint**

The primary endpoint of the study is the cumulated dose (mg) of oral targeted therapy during the 3-month follow-up.

#### **5.1.2 Assessment methods**

At each visit, patients should bring their oral targeted therapy packet delivered by their pharmacist (empty or started). Missing and remaining tablets will be counted by the medical team and reported in the CRF according to their dose.

The cumulated dose (mg) of the oral targeted therapy, taken between 2 visits, will be calculated as follows: sum of doses (mg) of the tablets used by the patient. Counting the tablets consumed by patients between consultations  $V_{i-1}$  and  $V_i$  will be done by the study team during consultation  $V_i$  from boxes of tablets returned by the patient. The doctor will report, in the CRF, and for each possible dosage (20 mg, 30 mg, 40 mg, 50 mg [only as second intention dose if the treatment is well-tolerated and as per product sheet recommendations]), the number of tablets used by the patient. The cumulated dose between consultations  $V_{i-1}$  and  $V_i$  will be calculated as follows:

$$[\text{Cumulated dose (mg)}]_i = \sum_{\text{Dosages in } \{20, 30, 40\}} [\text{Dosage} \times \text{Ntab(Dosage)}],$$

Where  $Ntab(Dosage)$  is the number of consumed tablets of 20 mg, 30 mg 40 mg or 50 mg respectively.

The cumulated dose (mg) of oral targeted therapy over the 3-month study will be equal to the sum of the cumulated doses (mg) taken between the 2 visits, during the 3-month study. The total cumulated dose (mg) over 3 months will be calculated as follows:

$$\text{Cumulated dose (mg)} = \sum_i [\text{Cumulated dose (mg)}]_i$$

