| 
satisfy the essential inclusion and exclusion criteria, and for whom information is available for the major evaluation criteria (in particular the primary criterion).
 
Statistical methods
 
The statistical analysis will be performed using SAS (version 9.1 or a more recent version). All tests will be performed 2-sided with a cut-off of 5%.
 
Analysis of the primary criterion
 
The primary objective of the study is to evaluate overall treatment compliance after 3-months and to compare this compliance between the 2 study groups: the group with nurse-led follow-up and the group without nurse-led follow-up.
 
The cumulated dose (mg) of oral targeted therapy taken between 2 visits will be calculated as follows: sum of the doses (mg) of the tablets taken by the patient. The count of taken tablets by the patient between visit Vi-1 and visit Vi will be done by the medical team investigator during visit Vi based on the tablet boxes returned by the patient. The physician will indicate in the Case Report Form (CRF) for each dosage (20 mg, 30 mg, 40 mg and 50 mg [only in 2nd intent dose if the treatment is well tolerated and according to the recommendations of the patient leaflet]), the number of tablets taken by the patient. The cumulated dose between visit Vi-1 and visit Vi will then be calculated as follows:
 $[\text{Cumulated dose (mg)}]_i = \sum_{\text{Dosages in 20, 30, 40, 50}} [\text{Dosage} \times \text{Number of tablets(Dosage)}]$ 
where Number of tablets is the number of tablets of 20mg, 30 mg, 40mg or 50mg taken.
 
The cumulated dose (mg) of oral targeted therapy taken during the 3-month follow-up will be the sum of the cumulated doses (mg) used between 2 visits during the 3-month follow-up. The total cumulated dose (mg) in 3 months will be calculated as follows:
 $\text{Cumulated dose (mg)} = \sum_i [\text{Cumulated Dose (mg)}]_i$ 
As such, the cumulated dose (mg) of the oral targeted therapy over the 3-month follow-up will be described for each groups (number of observed values, mean, standard deviation, median, lower quartile, upper quartile, minimum, maximum, two-sided 95% confidence interval of the mean).
 
The mean cumulated dose will be compared between groups by Student test, or Wilcoxon rank sum test in case of non-normal data or non-homogeneity of variance.
 
A complementary analysis using a Kaplan-Meier curve will also be performed on the principal criteria, to evaluate the time between start of treatment and the first dose modification or interruption of the targeted oral therapy.
 
The main analysis will also be completed by a descriptive analysis of the reasons for non-compliance. The numbers of the temporary and/or definitive stops due to the patient and/or to the investigator will be tabulated. Reasons will be listed.
 
Sample size
 |                                 |                               |                           |

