## **7.6 DETERMINATION OF SAMPLE SIZE**

In the absence of dose discontinuation or reduction, the cumulated dose of oral targeted therapy should be 3600 mg of afatinib, which corresponds to a daily dose of 40 mg for 90 days.

Clinical trials performed with afatinib before its marketing authorisation showed that over the first 3-month follow-up the mean dose of 3000 mg was taken (which corresponds to a dose intensity of 83%) (Boehringer Ingelheim First Interim Study Report 1200.32).

It was estimated that the mean dose observed in the group ‘without remote additional personalised nurse-led follow-up’ will be similar to the mean dose observed in the afatinib clinical trials and that adding an additional nurse-led follow-up will increase the mean dose by 6% (3180 mg, dose intensity of 88%).

As such, the number of patients to be included in the study has been calculated on the basis of a t-test for 2 unmatched samples with the following hypotheses:

- Mean cumulated dose of oral targeted therapy taken during the 3-month follow-up in the group ‘without remote additional personalised nurse-led follow-up’: 3000 mg (dose intensity of 83%).
- Mean cumulated dose of oral targeted therapy taken during the 3-month study in the group ‘with remote additional personalised nurse-led follow-up’: 3180 mg (dose intensity of 88%).
- Standard deviation of the cumulated dose of oral targeted therapy taken during the 3-month follow-up in both groups: 500.
- Type I error:  $\alpha = 0.05$ .
- Type II error:  $\beta = 0.20$  (power = 80%).
- Ratio ‘with remote additional personalised nurse-led follow-up’ group/‘without remote additional personalised nurse-led follow-up’ group = 3.

Using these hypotheses, in order to show an increase in the cumulated dose with the addition of 3-month nurse-led follow-up, it is necessary to have 82 patients in the group ‘without remote additional personalised nurse-led follow-up’ and 246 patients in the group ‘with remote additional personalised nurse-led follow-up’.

If it is considered that 20% of included patients will be non-evaluable for the primary criterion, it is necessary to include 99 patients in the group ‘without remote additional personalised nurse-led follow-up’ and 297 patients in the group ‘with remote additional personalised nurse-led follow-up’, i.e. 396 patients in total which can be rounded up to 400.

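### The Section 5.1.2 formula for the primary endpoint omits 50 mg tablets, against its own legend, the CRF instruction and the Synopsis: probably a slip, but one to correct before the endpoint is programmed

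*Combined protocol and SAP*

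**What the plan says.** Section 5.1.2 describes the calculation of the primary endpoint in four ways.

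- In words, the dose between two visits is the "sum of doses (mg) of the tablets used by the patient". No strength is excluded.
- For data capture, the physician enters tablet counts in the CRF "for each possible dosage (20 mg, 30 mg, 40 mg, 50 mg [only as second intention dose if the treatment is well-tolerated" (the remainder of the bracket refers to the product information).
- The displayed formula sums dosage times number of tablets over a set that the file renders as "Dosages in } \{20, 30, 40". There is no 50.
- The legend under the formula says that the tablet count "is the number of consumed tablets of 20 mg, 30 mg 40 mg or 50 mg respectively".

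The Synopsis gives the same endpoint with the set "Dosages in 20, 30, 40, 50" and the legend "where Number of tablets is the number of tablets of 20mg, 30 mg, 40mg or 50mg taken". Section 7.3.2, which sets out the primary analysis, has no formula of its own, so Section 5.1.2 holds the only formula in the body of the protocol.

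The scale of the endpoint comes from Section 7.6. Without interruption or reduction the cumulated dose "should be 3600 mg of afatinib, which corresponds to a daily dose of 40 mg for 90 days". The control mean is taken as 3000 mg, and nurse follow-up "will increase the mean dose by 6% (3180 mg, dose intensity of 88"%). The SD is 500 mg in both groups.

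**The concern.** Two formulas are printed for one primary endpoint, and they give different values for any patient who takes a 50 mg tablet. The Section 5.1.2 version credits that tablet with nothing. Section 5.1.2 links the 50 mg strength to good tolerance, so the patients affected would be ones who were taking their treatment, and they would be scored as if they had stopped.

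Three things would be at stake if the printed set reached the analysis program:

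- **Spread.** The false low values would widen the distribution and cost power. The Wilcoxon test named as the fallback in Section 7.3.2 would not remove the problem, because the affected patients' ranks would be wrong as well.
- **Bias.** If use of 50 mg differed between arms, the comparison would move against the arm that used it more.
- **The predictor model.** Section 7.3.3 classes a patient as non-compliant when the dose taken is strictly less than 80% of the uninterrupted, unreduced dose. A fully compliant patient could be misclassified.

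**Working it through.** **1. The plan's own figures.** 40 mg x 90 days = 3600 mg; 3000/3600 = 83.3%; 3180/3600 = 88.3%. For the two-sided 5% t-test with 82 and 246 evaluable patients, the standard error is 500 x sqrt(1/82 + 1/246) = 63.8 mg, the noncentrality is 180/63.8 = 2.82 on 326 degrees of freedom, and power is 80.4%. With 81 controls it is 79.9%. The stated 82/246 is reproduced.

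**2. One patient under each set.** Assume full intake for 90 days, d of them on one 50 mg tablet a day and the rest at 40 mg.

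- Set {20, 30, 40}: 40 x (90 - d)
- Set {20, 30, 40, 50}: 40 x (90 - d) + 50 x d

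| Days at 50 mg | As printed in 5.1.2 | As in Synopsis | Lost | Printed value / 3600 |
|---|---|---|---|---|
| 15 | 3000 | 3750 | 750 | 83.3% |
| 18 | 2880 | 3780 | 900 | 80.0% |
| 19 | 2840 | 3790 | 950 | 78.9% |
| 30 | 2400 | 3900 | 1500 | 66.7% |
| 60 | 1200 | 4200 | 3000 | 33.3% |

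With 3600 mg as the denominator, a fully compliant patient falls strictly below the 80% cut-off from 19 days at 50 mg.

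**3. Effect on power, under assumptions.** The documents give neither the share of patients reaching 50 mg nor the time spent there. Assume that a share p of both arms has the 60-day pattern, scored at v (1200 as printed, 4200 if counted correctly), and that the rest follow the planning values. Then:

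- SD = sqrt[(1 - p) x 500² + p(1 - p) x (3000 - v)²], used for both arms;
- difference = 180 x (1 - p), because the share p has the same value in both arms.

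| p | Difference | SD, correct | Power, correct | SD, as printed | Power, as printed | Loss from the omission |
|---|---|---|---|---|---|---|
| 2% | 176.4 | 523 | 75% | 555 | 70% | about 5 points |
| 5% | 171.0 | 553 | 68% | 626 | 57% | about 11 points |

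The correct-counting columns are the proper comparator. Patients at 4200 mg widen the spread too, so part of the fall from 80% would occur with the right formula.

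**4. Effect on the mean difference, under assumptions.** Suppose that 5% of the nurse arm and none of the control arm had the pattern.

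- Counted correctly: nurse mean = 3180 + 0.05 x (4200 - 3180) = 3231; difference 231 mg.
- As printed: nurse mean = 3180 - 0.05 x (3180 - 1200) = 3180 - 99 = 3081; difference 81 mg.
- Shift due to the formula: 231 - 81 = 150 mg, which equals 5% x 3000 mg.

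**The case against.** The best reply is that the section corrects itself. Its verbal definition, CRF instruction and legend all admit 50 mg tablets, and the Synopsis prints the full set. Only one subscript disagrees. A programmer would have to follow that subscript and ignore everything around it. Counts of 50 mg tablets are collected either way, so nothing is lost and the derivation can be put right at any time before analysis. Sections 7.4 and 8.3.1 leave the SAP to be finalised before database lock. All of this stands: it makes a slip far more likely than a decision to exclude 50 mg, and it makes the 0 mg credit conditional on literal programming.

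It might also be said that the 50 was lost when the file was converted. That cannot be tested from the text, but the set is legible and closed, and nothing points to a missing element.

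A reader might infer more than the documents support:

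- **That Section 5.1.2 overrides the Synopsis.** Nothing in the documents ranks one above the other.
- **That the omission cuts power from 80% to 70% or 57%.** It does not. The right starting points under the same assumptions are 75% and 68%.
- **That 150 of the planned 180 mg would disappear.** The 150 mg is measured from the correctly counted 4200 mg. Measured from the planned nurse-arm mean of 3180 mg, the loss is 99 mg.
- **That the highest exposures become the lowest.** The example's 1200 mg equals 30 days at 40 mg, and patients who stop earlier score less.
- **That the SAP repeats the error.** No separate SAP derivation of this endpoint is in the file.

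**Conclusion.** The contradiction is real and lies in the definition of the primary endpoint. Section 5.1.2 prints a formula that disagrees with its own legend, CRF instruction and verbal definition, and with the Synopsis. It is most likely a drafting slip. Followed literally it is a wrong rule, so it should be corrected before anyone programs from it, especially in an open-label study where two printed definitions would leave room for a choice after the data are seen.

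The result for an individual patient follows by arithmetic from the printed set, given the assumed intake pattern. The 80% misclassification also takes 3600 mg as the reference dose, which Section 7.6 supports but Section 7.3.3 does not state as a number. The trial-level effects (about 5 or 11 points of power, or a shift of 150 mg) rest on assumed shares of 2% and 5%, an assumed 60 days at 50 mg, and, for the shift, an assumed 5-point difference between arms. They show scale and are not forecasts. If nobody took 50 mg, the two formulas would agree.

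**What to change.** In Section 5.1.2, change the summation set to {20, 30, 40, 50}, so that it matches the Synopsis formula and the legend below it. Carry that single definition into the SAP derivation, and use the same derived variable for the primary comparison and for the 80% ratio in Section 7.3.3.

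The cost is a one-term text correction. The CRF already captures 50 mg tablets, so no new data are needed, and the 82/246 calculation is unaffected. The change concerns the calculation of the endpoint only and has no bearing on dosing.
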